9.7 Adverse Events

The patients will be monitored throughout the study for any Adverse Events. AEs will be collected through both solicited and unsolicited means and subsequently coded in tabular form using the MedDRA (Version 19 or higher) Adverse Event Dictionary. The patients will be encouraged to report signs, symptoms, and any changes in health to the clinic staff. Severity of each AE will be determined by the staff based on observation and questioning of the patients. The Investigator will judge the relationship of the event to the study treatments. Adverse events should be followed up until they have resolved or stabilized.

9.7.1 Adverse Event Definitions

Adverse Event: Any untoward medical occurrence in a patient or clinical investigation patient administered a pharmaceutical product and which does not necessarily have a causal relationship with treatment. An AE can therefore be any unfavorable and unintended sign, symptom, or

CONFIDENTIAL PROTOCOL

An Open Label, Safety Study to Assess the Potential for Adrenal Suppression Following Maximal Use Treatment with Desoximetasone 0.25% shampoo(Taro Pharmaceuticals U.S.A., Inc.) in Patients with Scalp Psoriasis

disease, temporally associated with the use of a medicinal (investigational) product, whether or not related to this product. This includes events not seen at baseline, or worsened even if present at baseline.

Unexpected Adverse Event: An adverse event where the nature or severity of is not consistent with the applicable product information (e.g., Investigator's Brochure for an unapproved investigational product or package insert/summary of product characteristics for an approved product).

Adverse Drug Reaction: All noxious and unintended responses to a medical product related to any dose should be considered adverse drug reactions. The response to a 'medical product' means that a causal relationship between a medicinal product and an adverse event is at least a reasonable possibility, i.e., the relationship cannot be ruled out.

9.7.2 Severity of Adverse Event

The severity of the adverse event will be graded by the Investigator using the following criteria as guidelines:

- **MILD:** Awareness of symptom but does not interfere with routine activities.
- **MODERATE:** Discomfort sufficient to interfere with routine activities.
- **SEVERE:** Impossible to perform routine activities.

9.7.3 Relationship of Adverse Event

Relationship to the Study Product

- **NOT RELATED:** Any AE that is clearly not related to use of the study drug.
- **POSSIBLE:** The association of the AE with the study drug is unknown; however, a relationship between the drug and event cannot be ruled out.
- **PROBABLE:** There is reasonable temporal relationship between the use of the study drug and the AE. Based upon the Investigator's clinical experience, the association of the event with the study drug seems likely.
- **DEFINITE:** The AE occurs following the application of the study drug and it cannot be reasonably explained by any other known characteristics of the patient's clinical state, environmental or toxic factors, or other modes of treatment administered to the patient. It disappears or decreases upon discontinuation of the study medication and reappears on a re-challenge of the study drug.

9.7.4 Patient's Participation Stopping Criteria

In the opinion of the Investigator, if the patient suffers an AE that warrants discontinuation of the study drug because of interference with age-appropriate instrumental ADL (Activities of Daily Living), for example preparing for meal, shopping for groceries or clothing, using the telephone, etc. the patient will be followed until the AE resolves or is considered stable. Any subject that discontinues the study because of an adverse event will be followed until resolution or stabilization of the adverse event.

CONFIDENTIAL PROTOCOL

An Open Label, Safety Study to Assess the Potential for Adrenal Suppression Following Maximal Use Treatment with Desoximetasone 0.25% shampoo(Taro Pharmaceuticals U.S.A., Inc.) in Patients with Scalp Psoriasis

9.8 Serious Adverse Events

9.8.1 Definition of a Serious Adverse Event

A Serious Adverse Event (SAE) is any untoward medical occurrence that at any dose suggests a medically significant hazard, including any event that:

- Results in death: includes all deaths, even those that appear to be completely unrelated to study treatment (e.g., car accident where patient is a passenger).
- Is life-threatening: in the view of the Investigator, the patient is at immediate risk of death at the time of the event.
- Results in persistent or significant disability or incapacity (substantial disruption of one's ability to conduct normal life).
- Requires inpatient hospitalization or prolongation of existing hospitalization.
- Causes congenital anomaly or birth defect.
- Is an important medical event that may not be immediately life-threatening or result in death or hospitalization, but may jeopardize the patient or may require medical or surgical intervention to prevent one of the serious outcomes listed above (e.g., intensive treatment in an emergency room, convulsions that do not result in hospitalizations). Emergency Room visits that require medical or surgical intervention to prevent one of the other serious outcomes listed above are considered a Serious Adverse Event.

9.8.2 Reporting Serious Adverse Events

Investigator Reporting of SAEs

Adverse events that are evaluated by the Investigator as "Serious" will be reported to the Sponsor and IRB within 24 hours of notice whether or not they are considered expected or drug-related. All SAEs will be reported as per applicable regulations. All SAEs encountered during the study will be reported on the appropriate form and summarized in the final report.

Any serious or unexpected adverse events should be reported to Novum within 24 hours. Following is the contact information:

[name]
Vice President, Clinical Trials
[contact]
[contact] [name]
[contact]

Or
[name]
Medical Monitor
[contact] [name]
[contact]

Novum will report any Serious Adverse Event to Taro.

CONFIDENTIAL PROTOCOL

An Open Label, Safety Study to Assess the Potential for Adrenal Suppression Following Maximal Use Treatment with Desoximetasone 0.25% shampoo(Taro Pharmaceuticals U.S.A., Inc.) in Patients with Scalp Psoriasis

Documentation of serious or unexpected adverse events and follow-up information should be sent to Taro's SAE Coordinator and Taro's Drug Safety Manager within 24 hours from Novum being made aware of the SAE. Following is the contact information:

Taro SAE Coordinator:

[name]
Coordinator, Clinical Operation
Taro Pharmaceuticals USA Inc.
[contact] [name]
Email: [contact]

Taro Drug Safety Manager:

[name], BSN,
Associate Director, Drug Safety

Taro Pharmaceuticals U.S.A., Inc.
[contact] [name]
Email: [contact] and [contact]

The Sponsor must notify FDA of fatal or life threatening adverse event as soon as possible but no later than 7 calendar days from reporting the event by the Investigator. Investigators will be informed of any SAEs reported at other study sites within 15 days from the initial report. Investigators will be informed of any SAEs reported at other study sites within 15 days from the initial report.

10.0 STATISTICAL METHODS

10.1 Statistical Plan

A Statistical Analysis Plan (SAP), detailing the intended statistical analysis of the study data, will be prepared as a separate document and finalized before database lock. Any deviation from the original statistical plan will be described and justified in the final report, as appropriate. The procedure for accounting for missing, unused and spurious data will be included in the Statistical Analysis Plan.

All statistical analysis will be conducted using SAS®, Version 9.4 or higher.

10.1.1 Determination of Sample Size

The sample size of 20 evaluable patients was deemed appropriate to meet the objective of the study.

10.1.2 Safety Analysis of Potential HPA Axis Suppression

Dosing will be once daily for 28 days. Patients with normal adrenal function at baseline , use at least 21 doses of the study product and have data from a post-treatment cortisol response test will be included in the analysis. Patients who have not used 21 doses of the study product will be excluded from the primary analysis of HPA axis suppression.

The primary analysis of interest is to assess the proportion of patients considered to have demonstrated possible HPA axis suppression following treatment with the study medication. As a secondary analysis of the data a logistic regression of the proportion of patients in the study with HPA axis suppression will be performed with % scalp affected as a covariate. See Appendix D for results from the cortisol response test considered indicative of potential HPA axis suppression.

For all patients the actual amount of desoximetasone (mg) applied during the study will be calculated from recorded bottle weights and presented.

CONFIDENTIAL PROTOCOL

An Open Label, Safety Study to Assess the Potential for Adrenal Suppression Following Maximal Use Treatment with Desoximetasone 0.25% shampoo(Taro Pharmaceuticals U.S.A., Inc.) in Patients with Scalp Psoriasis

After completion of 20 patients an interim analysis will be performed and presented.

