4.0 SYNOPSIS

Protocol Number	DSXS 1538a
Title	An Open-Label, Safety Study to Assess the Potential for Adrenal Suppression Following Maximal Use Treatment with Desoximetasone 0.25% Shampoo (Taro Pharmaceuticals U.S.A., Inc.) in Patients with Moderate to Severe Scalp Psoriasis
Objectives	
The objectives of this study are to:
 
1. Evaluate the potential of desoximetasone 0.25% shampoo to suppress HPA axis function in patients with moderate to severe scalp psoriasis.2. Evaluate the efficacy parameters and adverse event (AE) profiles of desoximetasone 0.25% shampoo administered to patients with moderate to severe scalp psoriasis.
Sponsor	Taro Pharmaceuticals U.S.A., Inc.
Name of Test Product	Desoximetasone 0.25% shampoo
Route of Administration	Topical
Study Design	An open-label, safety study to assess the potential for adrenal suppression following maximal use treatment with desoximetasone 0.25% shampoo applied once-daily for 28 days in adult patients with moderate to severe scalp psoriasis. Each patient is expected to receive 28 doses of study product.
Study Population	Up to 40 patients will be enrolled to obtain 20 evaluable male or female patients 18 years of age or older with a confirmed diagnosis of moderate to severe plaque psoriasis of the scalp with $\geq 25\%$ scalp affected.
Study Conduct	All patients will attend the clinic for 3 scheduled visits and a telephone follow-up phone call (Visit 4): Visit 1: Screening /Enrollment (Day 1) Visit 2: Interim Visit (Day 14 ± 2) Visit 3: End of Study (Day 29 ± 2) or Early Termination Visit 4: Follow Up (Day 42 ± 4) Telephone Phone Call If 10 or more patients experience biochemical abnormal values suggestive of possible HPA axis suppression, enrollment will be stopped. Such abnormality is defined by a 30 minute post Cortrosyn™ injection level cortisol level of ≤ 18 mcg/100ml during the Cortisol Response Test.
Inclusion Criteria	
1. Male or non-pregnant, non-lactating females 18 years of age or older.2. If female and of childbearing potential, prepared to abstain from sexual

CONFIDENTIAL PROTOCOL

An Open Label, Safety Study to Assess the Potential for Adrenal Suppression Following Maximal Use Treatment with Desoximetasone 0.25% shampoo(Taro Pharmaceuticals U.S.A., Inc.) in Patients with Scalp Psoriasis

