	
biological therapies for psoriasis.
 
26. Inability to understand the protocol requirements, instructions, and study-related restrictions, the nature, scope, and possible consequences of the clinical study.
 
27. Unlikely to comply with the protocol requirements, instructions, and study-related restrictions, such as uncooperative attitude, inability to return for follow-up visits, and improbability of completing the clinical study.
 
28. Receipt of any drug as part of a research study within 30 days before baseline.
 
29. The patient is a member of the investigational study staff or a member of the family of the investigational study staff.
 
30. Previous participation in this study.

Criteria for Evaluation	
Primary Outcome Measures:
 
Hypothalamic Pituitary Adrenal (HPA) Axis Response to Cosyntropin demonstrating the absence or presence of adrenal suppression at the end of treatment defined by the following criteria: 30 minute post Cortrosyn™ injection level cortisol level of ≤ 18 mcg/100ml during the Cortisol Response Test
 
Secondary Outcome Measures:
 
Hypothalamic Pituitary Adrenal (HPA) Axis Response to Cosyntropin demonstrating the presence of adrenal suppression at the end of treatment with % Scalp Affected as a covariate

HPA Axis Evaluation	
If at the end of the study the patient has a cortisol response test that is suggestive of HPA axis suppression, they will have a follow up test at least every 4 weeks in accordance to the follow up calendar in Appendix D or until such time as the Investigator considers the adrenal function has turned to normal.
 
Patients with normal adrenal function at baseline will be included in the HPA Axis evaluation.
 
Primary Analysis:
 
Proportion of patients in the study with HPA axis suppression following treatment with the study medication.
 
Secondary Analysis:
 
A logistic regression of the proportion of patients in the study with HPA axis suppression will be performed with % scalp affected as a covariate.

Safety Parameters	Adverse events will be classified using standard MedDRA terminology Version 19 or higher and summarized over all patients. Adverse events reported during the study will be tabulated in summary table by type, date of onset, date of resolution, incidence, severity, action taken, outcome and Investigator's opinion of relationship to the study product will be prepared by

CONFIDENTIAL PROTOCOL

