9.3.4 Removal of Patients from the Study

Patients will be advised that they are free to withdraw from the study at any time for any reason or, if necessary, the Investigator may withdraw a patient from the study to protect the health of that patient. A patient may also be withdrawn for not complying with study procedures. The clinical report will include all reasons for early withdrawals.

CONFIDENTIAL PROTOCOL

An Open Label, Safety Study to Assess the Potential for Adrenal Suppression Following Maximal Use Treatment with Desoximetasone 0.25% shampoo(Taro Pharmaceuticals U.S.A., Inc.) in Patients with Scalp Psoriasis

All patients who administer at least one dose of randomized study medication will be included in the safety analysis. If a patient terminates from the study early, all efforts will be made to complete their next visit study procedures. In case of early termination the Investigator shall fully document the reason for early termination. Reasons for early termination may include the following:

- Patient withdrew consent
- Significant adverse event that led the Investigator or patient to withdraw for safety reasons
- Worsening signs/symptoms of scalp psoriasis
- Development of an intercurrent condition or complication that could affect the safety of the patient or the validity of the evaluation of the patient's clinical state to an extent considered significant by the Investigator
- Signs and symptoms of possible HPA axis suppression
- Protocol deviations/violations that in the Investigator's opinion warrant discontinuation

Non-compliance with dosing need not be a reason for early termination. Patients who withdraw or are removed from the study will not be replaced. In the event a patient withdraws or is dropped from the study for any reason, the Investigator will request return of the unused product and report the reason for the discontinued participation.

When a patient discontinues early from the study, all study procedures required for the end of study should be performed at their last study visit. Patients who are discontinued from the study will be evaluated for safety and will be given, or referred for, appropriate treatment.

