9.4 Treatments

9.4.1 Treatments Administration

The patient will be instructed to apply the study product to psoriasis-affected areas of the dry scalp once daily for 28 days. Patients are to move the hair away from the dry scalp so that one of the affected areas is exposed. A small amount of the study shampoo is to be applied directly to the affected area by gently squeezing the bottle. The shampoo is to be gently rubbed into the affected area. The same procedure is to be followed for other affected areas on the scalp. Patients will be instructed to use only enough to cover affected areas and avoid application to face, groin, armpits, lips or eyes. If during application the product comes in contact with the eyes or eyelids, patients will be instructed to rinse the area with abundant water immediately. Patients should not cover the head with a shower cap while the shampoo is on the scalp. The shampoo is to be left in place for 15 minutes before adding water, lathering and rinsing hair and scalp completely.

The patient will be instructed to apply the medication once daily until the patient's next scheduled visit. Each patient will be provided with a dosing diary in which they will be required to record dosing dates and times. These diaries should be brought to each visit so that the study staff may check compliance. At the end of the study, the dosing diaries will be retained in the patient's file as source documentation.

CONFIDENTIAL PROTOCOL

An Open Label, Safety Study to Assess the Potential for Adrenal Suppression Following Maximal Use Treatment with Desoximetasone 0.25% shampoo(Taro Pharmaceuticals U.S.A., Inc.) in Patients with Scalp Psoriasis

At Visit 1 qualified study patients will be provided with one 120 ml bottle of desoximetasone 0.25% shampoo along with instructions for dosing. This bottle should be weighed before dispensing and the weight recorded. At Visit 2, the bottle should be collected and weighed and a new 120 ml bottle of shampoo should be weighed and dispensed along with dosing instructions. This bottle will be returned and weighed at Visit 3.

Treatment compliance will be encouraged by instructing the patient on the proper dosing technique and by the use of the daily diary. Compliance will be assessed by evaluation of the diary.

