9.5 Study Conduct

The cortisol response test is to be done in the morning as the body's peak cortisol level is directly related to the event of awakening. Visit 1 and Visit 3 should be scheduled before noon and subjects should not apply the study drug within 12 hours of Visit 3.

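### The only planned HPA-suppression rate leaves out patients with fewer than 21 doses, although possible HPA suppression is a listed reason to stop early, and no supportive rate includes them

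*Protocol*

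**What the plan says.** **Analysis set.** Protocol 10.1.2 admits a patient to the HPA analysis on three conditions: adrenal function normal at baseline, at least 21 doses used, and a cortisol test after treatment. It adds: "Patients who have not used 21 doses of the study product will be excluded from the primary analysis of HPA axis suppression". SAP 6.2.1 repeats the three conditions. T16.1.9.4 is the only table of HPA suppression. Its denominator is that set, and it shows counts and percentages without intervals.

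**Synopsis.** The HPA Axis Evaluation entry gives only the first condition: "Patients with normal adrenal function at baseline will be included in the HPA Axis evaluation".

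**Safety Population.** SAP 5 defines this as everyone with at least one dose. The adverse event, laboratory shift, IGA and percent-scalp tables use it. No HPA rate does.

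**Early leavers.** Protocol 9.3.4 includes "Signs and symptoms of possible HPA axis suppression" among the reasons for early termination. For those who leave early, "all study procedures required for the end of study should be performed at their last study visit". Protocol 11.2.4 likewise has the Visit 3 case report form completed for them.

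**Spacing of tests.** Protocol 9.6.18 and Appendix D rule out a repeat Cortrosyn test within four weeks of the previous one.

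**Listings.** L16.2.3 lists patients excluded from the HPA analysis with the reason, L16.2.6.1 all cortisol results with a suppression flag, and L16.2.6.2 the follow-up tests. The last-dose date is in a separate listing, L16.2.5.1.

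**The concern.** The primary endpoint is a safety rate from about 20 patients, so each patient carries about 5 percentage points (1/20). The dose condition is applied after treatment starts, and one listed reason for failing it is clinical suspicion of the event being counted. Exclusion can therefore depend on the outcome. A tested, suppressed early stopper drops out of both numerator and denominator, and someone who reads only T16.1.9.4 could see 0% when a case exists in the listings.

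Protocol 10.1.2 excludes these patients only from the primary analysis, so a further rate is open to the plan, but none is specified. The SAP's missing-data rule (6.5) is to use available data. The optional logistic regression gives no rate below 21 doses.

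The spacing rule bears on the same patients. It affects whether, and how long after the last dose, an early stopper is tested at all.

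**Working it through.** **1. The threshold.** Protocol 9.6.15 sets the lower compliance limit at 75% of 28 scheduled doses: 0.75 × 28 = 21. The plan's figure reproduces.

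**2. What one patient can do to the rate.** The documents give no expected number of tested patients below 21 doses, so every count here is an assumption. The only rate they report is for the spray (Protocol 7.3), a different product and regimen: 1/12 and 2/9, together 3/21 = 14.3% (3.0 to 36.3). Intervals are exact (Clopper-Pearson) 95%: for x of n, the lower limit is the 0.025 quantile of Beta(x, n − x + 1) and the upper limit the 0.975 quantile of Beta(x + 1, n − x). With x = 0 the upper limit is 1 − 0.025^(1/n), so for n = 20 it is 16.8%.

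| 21-dose set | Added patients below 21 doses | Wider rate |
|---|---|---|
| 0/20 = 0% (0 to 16.8) | 1 suppressed | 1/21 = 4.8% (0.1 to 23.8) |
| 0/20 = 0% (0 to 16.8) | 1 suppressed, 4 not | 1/25 = 4.0% (0.1 to 20.4) |
| 3/20 = 15.0% (3.2 to 37.9) | 5 not suppressed | 3/25 = 12.0% (2.5 to 31.2) |
| 3/20 = 15.0% (3.2 to 37.9) | 1 suppressed, 5 not | 4/26 = 15.4% (4.4 to 34.9) |

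The rate can rise, fall or stay nearly the same, and the intervals overlap widely.

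**3. Who is affected.** Patients whose Visit 1 test already shows suppression are told to stop product, but they fail the baseline condition and belong in neither rate. The gap concerns baseline-normal patients who start treatment and stop short of 21 doses.

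**4. The four-week rule against the visit schedule.** Four weeks is 28 days, counted from the Day 1 test.
- Visit 3 window, Day 29 ± 2: Day 27 gives 27 − 1 = 26 days, Day 28 gives 27, Day 29 gives 28. Visits on Day 27 or 28 are inside the window but short of four weeks.
- A patient dosing daily from Day 1 with fewer than 21 doses has stopped by Day 20. A last visit on Day 20 is 20 − 1 = 19 days after the first test. Testing at that visit satisfies 9.3.4 and breaks the spacing rule; waiting does the reverse.

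**5. Time off drug at the test.** Take a patient in the primary set with doses on Days 1 to 21 and none after, the extreme case.
- If the four-week rule governs, the test falls on Days 29 to 31: 29 − 21 = 8 to 31 − 21 = 10 days.
- If it does not, the whole window is open: 27 − 21 = 6 to 10 days.

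For early stoppers, again only if the four-week rule governs, the test is no earlier than Day 29. A last dose on Day 7, 14 or 20 then means at least 22, 15 or 9 days off drug. If the rule does not govern, these minimums do not apply.

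**The case against.** The best defence is that nothing is concealed. Exclusions, cortisol values and follow-up tests are all listed for at most 40 patients, and symptoms recorded as adverse events enter the Safety Population tables. A 21-dose set is also a reasonable way to ask what happens under maximal use. Both points stand, which is why the primary set should stay. Neither supplies a rate.

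A second argument is that the link to the outcome is loose. Stopping would rest on non-specific symptoms, because no cortisol test is scheduled between Visits 1 and 3. Early stoppers might also be tested late, and Protocol 7.3 says recovery after withdrawal is usually rapid, so a wider rate could miss the case it was meant to catch. This also stands in part. It is a reason to show the time off drug beside each result, not to omit the rate. It also weighs against splitting about 20 patients into subgroup rates by that interval.

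Some stronger readings are tempting but unsupported:
- **That the rule understates suppression.** It also drops unsuppressed, under-dosed patients, so the net direction is open.
- **That early leavers go untested because Visit 2 has no cortisol test.** The request for next-visit procedures in 9.3.4 might suggest this. But Visit 3 is designated as the early-termination visit, and 9.3.4 and 11.2.4 both call for end-of-study procedures or forms.
- **That the enrollment-stopping count in the Synopsis contradicts the analysis set because it has no dose condition.** It is a safety trigger and need not share a denominator with the primary analysis.
- **That the 12-hour limit cannot affect who is counted.** Under 9.6.18 the end-of-study test is not done if the patient dosed within 12 hours, and no rescheduling rule is given, so a patient could be lost that way.

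The Synopsis difference is small. It also omits the test condition and reads as shorthand.

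**Conclusion.** The point holds as a gap in reporting, not as a fault in the choice of primary set. The plan gives one HPA-suppression rate. Entry to it can depend on suspected suppression, and no second rate shows whether the exclusion matters. How much it matters cannot be known from the documents: the effect depends on how many baseline-normal patients stop before 21 doses, how many of them are tested, and what those tests show. The move from 0% to 4.8% is the result of one assumed suppressed patient. It is material mainly because it separates no cases from one.

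The conflict between the four-week rule, the testing of early leavers and the first two days of the Visit 3 window is a separate inconsistency. It follows directly from the text and needs no assumed counts.

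**What to change.** 1. Keep the 21-dose set as primary. Beside T16.1.9.4, pre-specify a supportive rate in all baseline-normal patients with at least one dose and any post-dose cortisol test, whatever its result. Flag those who stopped for signs of HPA suppression. Give exact 95% intervals for both rates.
2. Add days from last dose to test to L16.2.6.1 as a descriptive column, without subgroup rates by interval.
3. Align the Synopsis entry with Protocol 10.1.2 and SAP 6.2.1.
4. Reconcile Protocol 9.3.4, 11.2.4 and the Visit 3 window with the four-week spacing rule in 9.6.18 and Appendix D, and state the result in the SAP.

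The analysis changes cost one extra table and one derived column, both from data already planned, and should be settled before database lock. The supportive rate has limits that should be stated with it: it mixes in lower exposure and possibly late tests, it includes early stoppers only if they are tested, and it may be less favourable than the primary rate.
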